8.1. Primary Efficacy Endpoint

The primary efficacy endpoint is the proportion of subjects with no evidence of cervical HSIL (i.e. no evidence of CIN2, CIN3) on histology (i.e. biopsies or excisional treatment)

and no evidence of HPV-16 and/or HPV-18 in cervical samples by type specific HPV testing at the Week 36 timeframe.

The primary hypothesis of superiority is:

H0: $\delta < 0$ vs. H1: $\delta > 0$.

where $\delta = Pv - Pp$, and Pv and Pp denote the true population probabilities of the primary endpoint for VGX-3100 and Placebo, respectively. The proportion in each treatment arm is calculated by the number of responders divided by the total number of responders and non-responders in the study population of the corresponding treatment arm. The detailed definitions of responder and non-responder are listed in Table 1.

For the primary endpoint, week 36 histology is evaluated based on the first biopsy or surgical excision procedure on or after Day 238; in case of multiple results on the same day, the one with worst grade will be used. The virology results used for analysis must be the latest result that is on or before the same date as the histology result and is taken on or after Day 238. If a subject undergoes excision or cervical biopsy at any time on or after Day 1 and before Day 238, the subject will be considered as non-responder.

Number of responders and non-responders, proportion of responders in each treatment arm, and difference of proportions between the two treatment arms will be presented. A p-value of superiority based on a test of risk difference and corresponding 95% confidence interval using the method of Miettinen and Nurminen [5] will be computed. Superiority will be concluded if the one-sided p-value is <0.025 and the corresponding lower bound of the 95% CI exceeds zero.

Responder proportion will also be summarized based on the stratification factors separately.

Table 1. Definition of Primary Endpoint Responder and Non-Responder

Responder	Non-Responder
	Subject with histologic evidence of cervical HSIL, Adenocarcinoma-in-situ (AIS), cervical carcinoma at Week 36
Subject with no histologic evidence of cervical HSIL ^a at Week 36 evaluation and no evidence of HPV-16 and/or HPV-18 at Week 36 ^b AND Subject in which an excision or biopsy sample ^c was NOT obtained between initial dose up to Week 36	OR Subject with evidence of HPV-16 or HPV-18 at Week 36 OR Subject in which an excision or biopsy sample was obtained between initial dose up to Week 36 OR Subjects with no Week 36 sample result

a. No evidence of HSIL is defined by histology as negative, squamous atypia, or LSIL

c. Excludes ECC-only samples

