4.1. Sample Size

A total of 198 subjects will be randomized to receive either 6 mg VGX-3100 or placebo IM followed by EP in a 2:1 ratio. This sample size provides 90% power to declare VGX-3100 superior to placebo, assuming the true proportion of subjects who achieve the primary endpoints is 35% and 14% for VGX-3100 and placebo, respectively. These proportions also incorporate missing data (~10%) classified as non-regressors (failures). The assumptions are based on the Phase 2 study results.

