4.2. Randomization, Stratification, and Blinding

Subjects will be randomized (2 VGX-3100:1 Placebo) in a stratified manner according to a) the degree of CIN observed in the biopsy specimens at screening (CIN2 vs. CIN3), b) Body Mass Index (BMI) category (≤25 vs. >25 kg/m2) on Day 0 visit, and c) age category (<25 years vs. ≥25 years) on Day 0 visit. There will be no pre-determined number of subjects required to be randomized within each stratum. To ensure that milder CIN2 disease is not over-represented in the study, the percentage of subjects enrolled with CIN2 will not exceed 50% of the total enrolled.

The study is double-blinded to both investigators and subjects.

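### The primary test and confidence interval do not use the three randomisation strata; the test stays valid, but it is mildly conservative and slightly imprecise if those factors are prognostic

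*SAP*

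**What the plan says.** Section 4.2 of the SAP randomises "in a stratified manner according to a) the degree of CIN observed in the biopsy specimens at screening (CIN2 vs. CIN3", and also by BMI (≤25 or >25 kg/m²) and age (<25 or ≥25 years). That makes 2 × 2 × 2 = 8 cells. The same section calls CIN2 the milder disease and caps it at 50% of enrolment.

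Section 8.1 defines each arm's proportion as responders over all responders and non-responders in that arm. It then plans "A p-value of superiority based on a test of risk difference and corresponding 95% confidence interval using the method of Miettinen and Nurminen", with this decision rule: "Superiority will be concluded if the one-sided p-value is <0.025 and the corresponding lower bound of the 95% CI exceeds zero". No strata, weights or covariates are named. The stratification factors reappear in the primary analysis only here: "Responder proportion will also be summarized based on the stratification factors separately".

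Section 8.2 carries the method over to the secondary efficacy endpoints, without p-values. No other planned analysis adjusts the treatment effect for the three factors. The mITT and PP analyses change the population, and the logistic models in Section 8.4 contain treatment arm and one marker result. Section 11 does not mention the matter.

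**The concern.** Stratified allocation removes most of the between-stratum variation from the difference between arms. A variance computed from the collapsed 2×2 table still counts that variation. If the factors predict response, the standard error is therefore overstated: the interval is wider than it needs to be, the test rejects less often under the null than its 2.5% allows, and some power is lost. The SAP hints that CIN grade is prognostic by capping the milder grade. It says nothing of the kind about BMI or age.

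What is at stake is efficiency. The sample size meets 90% power with almost nothing to spare, and the expected missing data already sit inside the assumed response rates as failures. A small gain that needs no further patients is therefore worth considering.

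**Working it through.** **Inputs from Section 4.1.** "A total of 198 subjects will be randomized to receive either 6 mg VGX-3100 or placebo IM followed by EP in a 2:1 ratio", so 132 v 66. The stated power is 90%, at assumed response rates of 35% (VGX-3100) and 14% (placebo). One-sided level 0.025 (Section 8.1).

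**Step 1: reproduce the plan's figure.**
- Pooled rate: (132 × 0.35 + 66 × 0.14)/198 = 55.44/198 = 0.28.
- Null SE: √[0.28 × 0.72 × (1/132 + 1/66)] = 0.0677.
- Alternative SE: √[0.35 × 0.65/132 + 0.14 × 0.86/66] = 0.0596.
- Power: Φ[(0.21 − 1.96 × 0.0677)/0.0596] = Φ(1.30) = 0.903.

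The same formula solved for N gives exactly 198. Exact enumeration of the unstratified Miettinen-Nurminen score test gives 0.908. The stated 90% holds and does not rely on stratification.

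**Step 2: where the excess variance comes from.** In one arm, crude variance p(1 − p) = within-stratum variance + between-stratum variance. As an illustration, assume CIN grades split 50:50 with response rates 45/25% on VGX-3100 and 20/8% on placebo.
- VGX-3100: crude 0.2275; within ½(0.45 × 0.55 + 0.25 × 0.75) = 0.2175.
- Placebo: crude 0.1204; within ½(0.20 × 0.80 + 0.08 × 0.92) = 0.1168.
- Stratified SE: √(0.2175/132 + 0.1168/66) = 0.0585, against 0.0596 crude. The CI half-width is 11.5 points against 11.7.

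**Step 3: all three factors.** The SAP gives neither stratum shares nor prognostic strengths, so all of these are assumptions. Shares: CIN3 60% for the simulation, 50% and 70% for the CI half-width; BMI >25 50%; age ≥25 75%. The simulation used 200,000 trials per scenario with permuted blocks of 6 within 8 strata. It compared the unstratified score test with the stratified one (Mantel-Haenszel weights). Size is one-sided at a common response rate of 28%; u = unstratified, s = stratified.

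| Odds ratios CIN/BMI/age | Power u | Power s | Size u | Size s | CI half-width u → s (points) |
|---|---|---|---|---|---|
| 1/1/1 | 0.906 | 0.904 | 0.0240 | 0.0238 | 11.7 → 11.7 |
| 1.5/1.25/1.25 | 0.905 | 0.906 | 0.0228 | 0.0233 | 11.7 → 11.6 |
| 2/1.5/1.5 | 0.909 | 0.914 | 0.0221 | 0.0237 | 11.7 → 11.5 |
| 3/2/2 | 0.915 | 0.929 | 0.0188 | 0.0237 | 11.7 → 11.2 |
| 4/3/3 | 0.920 | 0.944 | 0.0158 | 0.0239 | 11.7 → 10.8 |

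**Step 4: CIN grade only, 50:50.**

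| Assumed rates, VGX-3100 v placebo (%) | Power u (%) | Power s (%) |
|---|---|---|
| no CIN effect | 90.9 | 90.6 |
| 40/30 v 18/10 | 91.0 | 91.0 |
| 45/25 v 20/8 | 91.3 | 91.7 |
| 50/20 v 24/4 | 91.8 | 93.1 |

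The last row implies CIN odds ratios of (0.50/0.50)/(0.20/0.80) = 4.0 on VGX-3100 and (0.24/0.76)/(0.04/0.96) = 7.6 on placebo, which is an extreme case.

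**Step 5: separate discreteness from the strata.** With no strata effect at all, the exact one-sided size of the unstratified test is already 0.0225 at a common rate of 14% and 0.0242 at 28%. The large-sample size at 28%, which is free of discreteness, is 1 − Φ(1.96 × r), where r is the ratio of crude to within-stratum SE. With CIN3 at 50% it is 0.0250, 0.0243, 0.0229, 0.0199 and 0.0162 for the five rows of step 3. Only the fall from 0.0250 along that series is due to ignoring the strata.

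**Step 6: cell sizes.** The average is 66/8 ≈ 8 placebo subjects. The smallest cell under the assumed shares holds 66 × 0.5 × 0.5 × 0.25 = 4.1 (CIN3 at 50%) or 66 × 0.3 × 0.5 × 0.25 = 2.5 (CIN3 at 70%).

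**The case against.** The planned analysis contains no error. The hypothesis is stated on overall probabilities, the arm proportions are crude, and the sample size follows from an unstratified formula, so the SAP is consistent with itself. The test errs on the safe side. The gain is about half a power point under moderate assumptions and nil or slightly negative if the factors do not matter; it passes one point only with strong effects, for which the SAP offers no evidence. All of this stands, and it limits the weight of the point.

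A reader might go further in four ways that the SAP does not support.
- **That the test is invalid or the 90% power wrong.** The opposite is shown above.
- **That the whole shortfall from 2.5% comes from ignoring the strata.** Part is discreteness, and the stratified test also runs below 2.5%.
- **That the estimate is left exposed to chance imbalance in these factors.** Stratified allocation already balances them. In the moderate scenario the SD of the estimated difference is 0.0586 with either analysis.
- **That the precision is free.** Section 4.2 sets no minimum per stratum, and some cells may hold only 2 to 4 placebo subjects.

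Two further limits apply. The SAP never uses the word unstratified; that reading comes from the crude proportions and the absence of strata or weights. The protocol was not available for this review. Section 11 lists no change to the primary test, which suggests, but does not show, that the method follows the protocol.

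**Conclusion.** The point holds as an inexpensive improvement in efficiency, not as a validity error. A positive result under the current plan would stand. If the stratification factors are prognostic, the unstratified analysis is mildly conservative and its interval slightly wide. Stratifying would change power by −0.3 to +0.1 points with no or weak prognostic effect, about +0.5 with moderate effects and +1.3 to +2.4 with strong to very strong ones. With moderate or stronger effects, one-sided size is about 1.6–2.2% unstratified against 2.2–2.4% stratified.

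The direction is secure. The size rests on assumed prognostic strengths and stratum shares, and the SAP supports a prognostic role only for CIN grade, and only by implication. For the secondary endpoints the point concerns interval width alone.

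**What to change.** Before the group-level unblinded Week 36 summaries of Section 10 are produced, amend Section 8.1 as follows.
- Make the primary risk difference, 95% CI and p-value a stratified Miettinen-Nurminen analysis with Mantel-Haenszel weights.
- Use strata as randomised, and say so, because Section 6.1 expects stratification errors.
- Stratify by CIN grade at least. If all three factors are used, pre-specify how sparse or empty cells are pooled.
- Keep the unstratified result as a sensitivity analysis.

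In Section 8.2, apply the same stratified interval to the binary cervical endpoints.

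The cost is SAP wording and a programming option, with no new data. If the protocol also fixes the method, the change must be recorded in Section 11 or made in the protocol. The statistical price is sparse cells and a negligible loss of power (at most about 0.3 points in these scenarios) if the factors turn out not to be prognostic. Stratifying by CIN grade alone largely avoids the sparse cells.

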8.2. Secondary Efficacy Endpoints

For the secondary efficacy endpoints listed in Section 3.2.2 of this SAP, the analysis method will be the same as for the primary endpoint described in Section 8.1, but without p-values.

In addition, the definition of responder and non-responder for each endpoint is defined in Table 2.

b. The histopathologic efficacy time frame is defined by those who have undergone a biopsy or surgical excision at any time starting from 14 days prior to the protocol-specified target date of Week 36. The first tissue removal sample in this time frame determines the histology endpoint. The most recent HPV clearance result prior to tissue removal, which includes results from the same date, within the time frame determines the HPV clearance endpoint.

Table 2. Definition of Secondary Endpoints Responder and Non-Responder

Endpoint	Responder	Non-Responder					
Proportion of subjects with no evidence of cervical HSIL on histology (i.e. biopsies or excisional treatment) at Week 36 visit	Subject with no histologic evidence of cervical HSIL ^a at Week 36 ^b AND Subject in which an excision or biopsy sample ^c was NOT obtained between initial dose up to Week 36	Subject with histologic evidence of cervical HSIL, AIS, cervical carcinoma at Week 36 OR Subject in which an excision or biopsy sample was obtained between initial dose up to Week 36 OR Subjects with no Week 36 sample result					
Proportion of subjects with no evidence of HPV-16 and/or HPV-18 in cervical samples by type specific HPV testing at Week 36 visit	Subject with no evidence of HPV-16 and/or HPV-18 ^d at Week 36 AND Subject in which an excision or biopsy sample was NOT obtained between initial dose up to Week 36	Subject with evidence of HPV-16 or HPV-18 at Week 36 OR Subject in which an excision or biopsy sample was obtained between initial dose up to Week 36 OR Subjects with no Week 36 sample result					
Proportion of subjects with no evidence of squamous atypia, LSIL, or HSIL on histology (i.e. biopsies or excisional treatment) at Week 36 visit	Subject with no histologic evidence of cervical HSIL, squamous atypia, or LSIL ^e at Week 36 AND Subject in which an excision or biopsy sample was NOT obtained between initial dose up to Week 36	Subject with histologic evidence of cervical HSIL, squamous atypia, LSIL, AIS, cervical carcinoma at Week 36 OR Subject in which an excision or biopsy sample was obtained between initial dose up to Week 36 OR Subjects with no Week 36 sample result					

Proportion of subjects with no evidence of squamous atypia, LSIL or HSIL on histology (i.e. biopsies or excisional treatment) and no evidence of HPV-16 and/or HPV-18 by type specific HPV testing at Week 36 visit	Subject with no histologic evidence of cervical HSIL squamous atypia, or LSIL at Week 36 and no evidence of HPV-16 and/or HPV-18 at Week 36 AND Subject in which an excision or biopsy sample was NOT obtained between initial dose up to Week 36	Subject with histologic evidence of cervical HSIL, squamous atypia, or LSIL AIS, cervical carcinoma at Week 36 OR Subject with evidence of HPV-16 or HPV-18 at Week 36 OR Subject in which an excision or biopsy sample was obtained between initial dose up to Week 36						
		OR Subjects with no Week 36 sample result						
Proportion of subjects with no progression of cervical HSIL to cervical carcinoma from baseline on histology (i.e. biopsies or excisional treatment) at Week 36 visit	Subject with no histologic evidence of a worsening cervical condition at Week 36 relative to baseline AND Subject in which an excision or biopsy sample was NOT obtained between initial dose up to Week 36	Subject with histologic evidence of worsening of cervical condition at Week 36 relative to baseline OR Subject in which an excision or biopsy sample was obtained between initial dose up to Week 36 OR Subjects with no Week 36 sample result						
Proportion of subjects who have cleared HPV-16 and/or HPV-18 on specimens from non-cervical anatomic locations (i.e., oropharynx, vagina and intra-anal) at Week 36 visit	Subject with no evidence of HPV-16 and/or HPV-18 on specimens from non-cervical anatomic locations ^f at Week 36	Subject with evidence of HPV-16 or HPV-18 on specimens from non-cervical anatomic locations at Week 36 OR Subjects with no Week 36 sample result						

- a. No evidence of HSIL is defined by histology as negative, squamous atypia, or LSIL. The first tissue removal sample within the timeframe determines the histology endpoint.
- b. The efficacy time frame is defined by those who have undergone a biopsy or surgical excision at any time starting from 14 days prior to the protocol-specified target date of Week 36
- c. Excludes ECC-only samples
- d. The most recent HPV clearance result prior to first tissue removal, which includes results from the same date, within the time frame determines the HPV clearance endpoint.
- e. No evidence of squamous atypia, CIN1, CIN2 or CIN3 on biopsies or excisional treatment
- f. Based on HPV-16 and/or HPV-18 positive specimen at baseline. Subjects will be classified according to the presence/absence of HPV-16 and/or HPV-18 at baseline by each of the three anatomic locations.

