2.2. Secondary Objective

The secondary objectives of this study are:

- 1. Evaluate the safety and tolerability of VGX-3100 delivered intramuscularly (IM) followed by Electroporation (EP) with CELLECTRATM 5PSP
- 2. Determine VGX-3100 efficacy compared to placebo as measured by histopathologic regression of cervical HSIL
- 3. Determine VGX-3100 efficacy compared to placebo as measured by virologic clearance of HPV-16 and/or HPV-18
- 4. Determine VGX-3100 efficacy compared to placebo as measured by complete histopathologic regression of cervical HSIL to normal
- 5. Determine VGX-3100 efficacy compared to placebo as measured by both complete histopathologic regression of cervical HSIL to normal and virologic clearance of HPV-16 and/or HPV-18
- 6. Determine VGX-3100 efficacy compared to placebo as measured by histopathologic non-progression
- 7. Describe the clearance of HPV-16 and/or HPV-18 infection from non-cervical anatomic locations
- 8. Determine the humoral and cellular immune response following administration of VGX-3100 compared with placebo at post dose 3 and Week 36 visits as assessed relative to baseline

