3.1. Overall Study Design and Plan

HPV-301 is a prospective, randomized, double-blind, placebo controlled, multi-center study to determine the efficacy, safety, and tolerability of VGX-3100 administered by IM injection followed by EP delivered with CELLECTRA™ 5PSP in adult women with histologically confirmed cervical HSIL (CIN2, CIN3) associated with HPV-16/18.

A sample of approximately 198 subjects will be randomized to receive either 6 mg (in 1 ml) VGX-3100 or placebo, each IM followed by EP, in a 2:1 ratio in a stratified manner. To be eligible for the study, subjects age 18 years and above must consent to participate and have cervical biopsy/biopsies of the cervical lesion(s) at the time of screening. Slides of the biopsy will be sent to a Pathology Adjudication Committee (PAC) in a blinded manner to establish the presence of cervical HSIL within screening. In order to be eligible for continued enrollment, the PAC must assign the histologic diagnosis of cervical HSIL. Subjects must also have a cervical specimen test positive for HPV-16 and/or 18 by cobasTM HPV test to be eligible for participation in the study. The Schedule of Events in Appendix 13.1 provides the details of sample collection and assessment.

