3.2.2. Secondary Endpoints

The secondary endpoints of this study are:

- 1. a. Incidence and severity of local and systemic events for 7 and 28 days following each investigational treatment and for the duration of the study (through Week 88 visit)
 - b. Incidence and severity of all adverse events including SAEs, SUSAR, UADE and other unexpected AEs for the duration of the study (through Week 88 visit)
- 2. Proportion of subjects with no evidence of cervical HSIL on histology (i.e. biopsies or excisional treatment) at Week 36 visit
- 3. Proportion of subjects with no evidence of HPV-16 and/or HPV-18 in cervical samples by type specific HPV testing at Week 36 visit
- 4. Proportion of subjects with no evidence of Low grade squamous intraepithelial lesion (LSIL) or HSIL (i.e. no evidence of CIN1, CIN2 or CIN3) on histology (i.e. biopsies or excisional treatment) at Week 36 visit

- 5. Proportion of subjects with no evidence of LSIL or HSIL (i.e. no evidence of CIN1, CIN2 or CIN3 on biopsies or excisional treatment) on histology (i.e. biopsies or excisional treatment) and no evidence of HPV-16 and/or HPV-18 by type specific HPV testing at Week 36 visit
- 6. Proportion of subjects with no progression of cervical HSIL to cervical carcinoma from baseline on histology (i.e. biopsies or excisional treatment) at Week 36 visit
- 7. Proportion of subjects who have cleared HPV-16 and/or HPV-18 on specimens from non-cervical anatomic locations (oropharynx, vagina and intra-anal) at Week 36 Visit
- 8. a. Levels of serum anti-HPV-16 and anti-HPV-18 antibody concentrations at Week 15 and 36 visits
 - b. Interferon-γ ELISpot response magnitudes at baseline, Weeks 15 and 36 visits
 - c. Flow Cytometry response magnitudes at baseline and Week 15 visits

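### The non-progression endpoint is named as progression to carcinoma but scored on any histologic worsening, a term the SAP does not define

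*SAP*

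**What the plan says.** The SAP describes this endpoint in four places.

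- **Section 2.2, objective 6**, is general: "Determine VGX-3100 efficacy compared to placebo as measured by histopathologic non-progression". Item f) of the Week 36 release in Section 10 is equally general.
- **Section 3.2.2, item 6**, names a specific event: "Proportion of subjects with no progression of cervical HSIL to cervical carcinoma from baseline on histology (i.e. biopsies or excisional treatment) at Week 36 visit". The endpoint column of the Table 2 row carries the same name.
- **Section 8.2, Table 2, responder column**, reads "Subject with no histologic evidence of a worsening cervical condition at Week 36 relative to baseline", combined with the condition that no biopsy or excision was taken earlier.
- **Section 8.2, Table 2, non-responder column**, reads "Subject with histologic evidence of worsening of cervical condition at Week 36 relative to baseline", or an earlier procedure, or no Week 36 sample.

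Section 8.2 makes the table the operative text: "the definition of responder and non-responder for each endpoint is defined in" Table 2. Footnotes a to f do not define worsening. The other cervical histology rows name the categories that count as failure (HSIL, AIS, carcinoma and, where relevant, LSIL and squamous atypia). Only this row relies on an undefined comparison with baseline.

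**The concern.** The name and the rule describe different events. Every subject enters with HSIL, which spans two grades: "adult women with histologically confirmed cervical HSIL (CIN2, CIN3) associated with HPV-16/18". A CIN2 subject found to have CIN3 at Week 36 still has HSIL and does not have carcinoma, so by the name she has not progressed. By the rule she has worsened and is a failure.

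At stake is whether a named secondary result means what its label says. A reader of the report would take the proportion as freedom from carcinoma, while the scoring columns would have produced freedom from any worsening. The same row feeds the ITT, mITT and PP analyses and the subgroup analysis by prior HPV vaccination (Section 8). It is also item f) of the group-level unblinded release. The conditions in Section 10 for withholding an item depend on event counts, so the definition enters those too. If the wording is settled after group-level results are known, the choice is open to the criticism that it was made with the data in view.

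**Working it through.** **Step 1. The plan's own figure.** The SAP gives no expected rate or precision for non-progression. Its only sample-size figure is 198 in a 2:1 ratio for the primary endpoint (Section 4.1: 35% against 14%, 90% power; Section 8.1: one-sided 0.025). With pooled variance under the null and no continuity correction, the pooled proportion is (0.14 + 2 × 0.35)/3 = 0.28, and

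n(placebo) = [1.960 × √(1.5 × 0.28 × 0.72) + 1.282 × √(0.14 × 0.86 + 0.35 × 0.65/2)]² / 0.21² = (1.078 + 0.620)² / 0.0441 ≈ 65.4, rounded up to 66.

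The total is 3 × 66 = 198, with power 0.903. The figure reproduces and does not depend on the non-progression row. Below, 198 serves only as the denominator.

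**Step 2. How the SAP ranks histology.** Section 4.2 says: "To ensure that milder CIN2 disease is not over-represented in the study, the percentage of subjects enrolled with CIN2 will not exceed 50" (percent of the total). It also stratifies on CIN2 against CIN3. Section 8.1 uses the worst grade when several results fall on one day. CIN3 is thus worse than CIN2 in the document's own terms. Tables 1 and 2 list AIS separately from carcinoma.

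**Step 3. Name and rule side by side.**

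| Baseline to Week 36 | By the name | By the Table 2 rule |
|---|---|---|
| Same or lower grade | Success | Success |
| CIN2 to CIN3 | Success | Failure |
| CIN2 or CIN3 to AIS | Success | Failure, if AIS ranks above HSIL (not stated) |
| CIN2 or CIN3 to carcinoma | Failure | Failure |
| Earlier biopsy or excision, or no Week 36 sample | Failure (Table 2 convention) | Failure |

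The two disagree in the second and third rows. Subjects in the last row fail whichever histologic event is used and cannot switch.

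**Step 4. Illustrative size.** Let s be the CIN2 share of enrolment and q the proportion of CIN2 subjects with an evaluable CIN3 result at Week 36. Then

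subjects scored differently = 198 × s × q; change in the overall proportion = 100 × s × q percentage points.

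The SAP fixes only the upper limit of s, at 50%. The lower values of s and all values of q are assumptions.

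| s | q = 5% | q = 10% | q = 20% | q = 30% |
|---|---|---|---|---|
| 20% | 2.0 (1.0) | 4.0 (2.0) | 7.9 (4.0) | 11.9 (6.0) |
| 35% | 3.5 (1.8) | 6.9 (3.5) | 13.9 (7.0) | 20.8 (10.5) |
| 50% | 5.0 (2.5) | 9.9 (5.0) | 19.8 (10.0) | 29.7 (15.0) |

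Cells show subjects of 198, with percentage points in brackets. Changes from HSIL to AIS would add to these counts and are not included.

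**Step 5. Effect on the comparison.** One reclassified subject moves the placebo proportion by 1/66 = 1.5 points and the VGX-3100 proportion by 1/132 = 0.8 points. The shift in the treatment difference depends on how q differs between arms, which the SAP does not give.

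**The case against.** **Table 2 governs.** Section 8.2 sends the reader to Table 2 for scoring, and both scoring columns agree on worsening. This stands in part: it shows which text a programmer should follow. It does not rescue the label, which then describes a narrower event than the one counted, and it leaves worsening undefined.

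**HSIL could be read as one tier.** Eligibility rests on a single diagnosis of HSIL, so CIN2 to CIN3 might not count as worsening. The SAP's own grading (Step 2) makes this the weaker reading. That it is possible at all shows that the rule needs a list of transitions.

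**The consequence is limited.** This is one secondary endpoint reported without a p-value. That stands and sets the priority.

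Three stronger inferences are tempting, but the document does not support them:

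- *Half the sample is in play.* The 50% cap on CIN2 is a ceiling, not an expected share, and only CIN2 subjects who actually show a worse grade could switch.
- *Section 11 is silent, so this departs from the protocol.* Section 11 lists changes from a protocol that is not at hand. The same wording may already stand there.
- *The figure mainly measures missing data.* Counting missing results and early procedures as failures is the declared ITT convention (Section 4.3.1). The mITT analysis drops subjects without the endpoint, and the additional PP analyses use the Week 36 result despite earlier procedures (Sections 4.3.2, 4.3.3 and 8).

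**Conclusion.** The contradiction is real and sits within one row of Table 2. Followed as written, the plan reports freedom from any worsening under the name of freedom from carcinoma, with worsening left for the programmer to interpret.

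The size cannot be computed from the SAP. About 2 to 30 of 198 subjects (1 to 15 points of the overall proportion) is an illustration. It rests on an assumed CIN2-to-CIN3 rate of 5% to 30% and a CIN2 share from an assumed 20% up to the cap.

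A reader might infer that the carcinoma wording must be the right one because it appears twice. The documents do not settle that: objective 6 and item f) say only non-progression, which either concept fits. The finding is that the passages must agree, not that one of them is correct. It should be fixed before the Week 36 release. It does not bear on the primary endpoint, the power or the type I error.

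**What to change.** Before the group-level Week 36 release:

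1. Use one definition in Section 3.2.2 item 6 and in the endpoint, responder and non-responder columns of the Table 2 row.
2. Add a footnote stating, for each of CIN2 to CIN3, HSIL to AIS, and HSIL to carcinoma, whether it counts as progression.
3. If both concepts are wanted, report them as two separately named rows, one for progression to carcinoma and one for any histologic worsening, and state which of them is item f) in Section 10.

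The cost is SAP wording and at most one extra table row. No new data, visits or subjects are needed.
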